7.3 Method of Treatment Assignment

Subjects will be enrolled sequentially in Part A with no more than one subject enrolled per day into dose escalation cohorts. Enrollment in Part B will be stratified by disease cohort and dosing schedule, as applicable.

An IRT system will be used to track subject assignments to the dose levels in dose escalation (Part A) and cohorts in dose expansion (Part B).

7.4 Packaging and Labeling

The label(s) for CC-90009 will include sponsor name, address and telephone number, the protocol number, dosage form and strength (where applicable), lot number, expiry date (where applicable), medication identification/kit number, dosing instructions, storage conditions, and required caution statements and/or regulatory statements as applicable. Additional information may be included on the label as applicable per local regulations. Gen 2b material will be clearly labeled as Gen 2b. Labeling for each formulation will be color coded as per the Pharmacy Manual for that formulation.

7.5 Investigational Product Accountability and Disposal

Celgene (or designee) will review with the Investigator and relevant site personnel the process for investigational product return, disposal, and/or destruction including responsibilities for the site versus Celgene (or designee).

7.6 Investigational Product Compliance

Only the pharmacist or the Investigator's designee will dispense CC-90009. A record of the total dose (and number of vials used) of CC-90009 administered to each subject must be maintained.

The pharmacist or Investigator's designee will document the doses dispensed/administered in the appropriate study records and the appropriate eCRF.

8 CONCOMITANT MEDICATIONS AND PROCEDURES

All medications (excluding prior cancer therapy for the tumor under evaluation) taken beginning when the subject signs the ICD and all concomitant therapy during the study until 28 days after treatment discontinuation, together with dose, dose frequency and reasons for therapy use will be documented in the source documents and on the concomitant medication eCRF.

All prior cancer therapy for the tumor under evaluation, including chemotherapy, biologic, immunologic, irradiation, and surgery, will be documented on dedicated prior cancer treatment eCRFs.

The Investigator will instruct subjects to notify the study staff about any new medications taken after signing the ICD. All medications and significant non-drug therapies (herbal medicines, physical therapy, etc.) and any changes in dosing with existing medications will be documented on the eCRFs.

8.1 Permitted Concomitant Medications and Procedures

Subject to the precautions described in Section 8.2, the use of any concomitant medication/therapies deemed necessary for the care of the subject should be used. Repeat PK evaluations may be conducted if changes are made to concomitant medications suspected of affecting drug absorption or metabolism.

Medications to prevent or treat TLS are permitted. Medications may include hypouricemic agents (eg, allopurinol, rasburicase), diuretics, and phosphate and potassium binders. Rasburicase is contraindicated in subjects with screening G6PD deficiency.

Medications to treat infusion reactions are permitted. Medications may include antihistamines, H2-blockers, anti-pyretics, corticosteroids, bronchodilators and other medications as medically indicated.

Routine prophylaxis with granulocyte colony stimulating factor or granulocyte-macrophage colony stimulating factor is allowed at the Investigator's discretion after Cycle 1.

Subjects receiving recombinant erythropoietin or darbepoetin alfa for at least 4 weeks prior to starting the CC-90009 may continue their pretreatment doses throughout the study.

Leukapheresis to control leukocytosis is permitted unless it is within the 2 weeks prior to the first dose of CC-90009. In Cycles 1-4, leukapheresis cannot be performed the same day as CC-90009 dosing.

Hydroxyurea to control leukocytosis is permitted during screening and Cycle 1 at the Investigator's discretion.

Parenteral flu vaccination is permitted.

Routine infectious disease prophylaxis including appropriate prophylactic antibiotic, antiviral, antipneumocystis, antifungal, or other prophylaxis should be implemented during the study according to institutional standard medical practice.

Subjects may receive approved or authorized COVID-19 vaccines while continuing on study treatment at the discretion of the Investigator. COVID-19 vaccines that are NOT live are allowed and should be handled in the same manner as other vaccines. Administration may occur during the study, including during the administration of the BMS study treatment and after the last administration of the BMS study treatment.

Treatment of active SARS-CoV-2 infections or high risk exposures, including use of investigational therapies, is allowed and should be discussed with the Sponsor Medical Monitor.

Even though CC-90009 is not anticipated to cause drug interactions when administered with CYP2C9 and CYP2C19 substrates at clinically relevant concentrations, caution should be used with narrow therapeutic index substrates such as warfarin, clopidogrel, voriconazole, phenytoin, fluindione and acenocoumarol, consistent with general clinical practice.

8.2 **Prohibited Concomitant Medications and Procedures**

Other investigational therapies must not be used while the subject is on the study.

Anticancer therapy (chemotherapy, biologic or investigational therapy, and surgery), other than the study treatments and hydroxyurea during Cycle 1, must not be given to subjects while the subject is on the study. If such treatment is required the subject must be discontinued from the study. Focal palliative radiotherapy for treatment of cancer-related symptoms is allowed during study treatment at the discretion of the Investigator. Maintenance hormonal therapies are allowed in subjects with a history of breast or prostate cancer.

Treatment with chronic, therapeutic dosing of anti-coagulants (eg, warfarin, low molecular weight heparin, Factor Xa inhibitors) should be used with caution based on an overall risk-benefit assessment. Short-term, prophylactic dosing of anticoagulants may be considered in subjects if medically indicated (eg, hospitalized patients, post-operatively).

Administration of investigational (not approved or authorized by relevant health authorities) COVID-19 vaccines is not allowed during the study. Live COVID-19 vaccines should not be administered to a subject during the study, including during the treatment, safety follow-up period and within 3 months following the last dose of study drug. In addition, the administration of a live COVID-19 vaccine is prohibited at least 14 days prior to initiation of study treatment.

Concomitant use with a strong CYP3A4 inhibitor increases CC-90009 exposure, which may increase CC-90009 toxicities, including the risk of sepsis. Avoid concomitant use of CC-90009 with strong CYP3A4 inhibitors if possible. Alternative treatments for anti-fungal prophylaxis or medication (eg, micafungin, caspofungin, or amphotericin) should be considered. If concomitant use of strong CYP3A4 inhibitors is unavoidable during study treatment, CC-90009 dose reductions are required (Section 7.2.15) and subjects should be monitored closely for signs of toxicities. Subjects can resume CC-90009 at the dose used prior to initiation of the concomitant strong CYP3A4 inhibitor 3 days after discontinuation of the inhibitor.

• Examples of strong CYP3A4 inhibiting medications: Atazanavir, boceprevir, clarithromycin, cobicistat, conivaptan, danoprevir/ritonavir, darunavir, elvitegravir/ritonavir, indinavir, itraconazole, ketoconazole, lonafarnib, lopinavir/ritonavir, mibefradil, mifepristone,

nefazodone, nelfinavir, paritaprevir/ritonavir combinations, posaconazole, ritonavir, saquinavir, telaprevir, telithromycin, tipranavir/ritonavir, troleandomycin, voriconazole

Concomitant use with a strong or moderate CYP3A4 inducer may decrease CC-90009 efficacy. Avoid concomitant use of CC-90009 with strong or moderate CYP3A4 inducers. Alternative treatments with less CYP3A4 induction should be considered.

- Strong CYP3A4 inducers: avasimibe, carbamazepine (Tegretol[®]), enzalutamine, mitotane, phenytoin (Dilantin[®]), rifampin (Rifadin[®]), St. John's wort
- Moderate CYP3A4 inducers: bosentan, efavirenz, etravirine, modafinil, nafcillin

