6.3.2 Efficacy Long Term Follow-up

Subjects without documented progression of disease (or relapse) or start of new anti-cancer therapies will have efficacy evaluations of complete blood counts and peripheral blood smears performed every subsequent 8 weeks (± 1 week) for the 1st year and every 12 weeks (± 2 weeks) for the 2nd year or until progression of disease (or relapse), initiation of a new anticancer therapy, withdrawal from the study, death, or the End of Trial, whichever comes first. A bone marrow evaluation will be completed at the end of the 1st year and as clinically indicated during the Follow-up Period.

Information (including dates) on new anticancer therapies initiated will be collected until progression of disease (or relapse), withdrawal from the study, death, or the End of Trial, whichever comes first.

Information will also be collected on any study drug-related SAEs.

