6.3.3 Survival Follow-up

After the Safety Follow-up visit, all subjects will be followed according to the schedule for the efficacy long term follow-up (refer to Section 6.3.2) for survival for up to 2 years or until death, lost to follow-up, or the End of Trial, whichever occurs first. Survival follow-up may be conducted by record review (including public records) and/or telephone contact with the subject, family, or the subject's treating physician.

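### Section 8.2 takes a subject who needs other anticancer therapy off the study, which, read literally, conflicts with survival follow-up of all subjects in Section 6.3.3

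*Combined protocol and SAP*

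**What the plan says.** **Section 8.2** bars other anticancer therapy while a subject is on the study, apart from hydroxyurea in Cycle 1. It then adds: "If such treatment is required the subject must be discontinued from the study". Its next sentence, on palliative radiotherapy, refers to study treatment instead, so the section itself uses both terms.

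**Section 6.3.3** says: "After the Safety Follow-up visit, all subjects will be followed according to the schedule for the efficacy long term follow-up", and continues "for survival for up to 2 years or until death, lost to follow-up, or the End of Trial, whichever occurs first". On method: "Survival follow-up may be conducted by record review (including public records) and/or telephone contact with the subject, family, or the subject's treating physician". The Follow-up Period text in the Protocol Summary and Section 3.1 gives the same rule.

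**Section 6.3.2** ends efficacy evaluations at progression or relapse, or at "initiation of a new anticancer therapy, withdrawal from the study, death, or the End of Trial, whichever comes first". It also states: "Information (including dates) on new anticancer therapies initiated will be collected until progression of disease (or relapse), withdrawal from the study, death"; trial end is the last item in that list.

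**Section 6.3.1** follows all subjects for adverse events for 28 days after the last dose.

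**Tables 7 and 36** follow HR-MDS subjects for transformation to AML until death, loss to follow-up, withdrawal of consent for further data or end of trial.

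**Sections 11.1 and 11.2** give separate lists of reasons for stopping the investigational product and for leaving the study. New anticancer therapy is not named in the study list, though that list includes physician decision and an open category.

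**Section 9.6.2** plans Kaplan-Meier estimates of OS and refers to the SAP for full efficacy detail. No OS censoring rule appears in the supplied text.

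**The concern.** Sites hold two instructions that cannot both be followed literally, and the one in Section 8.2 is mandatory. If a site takes a subject off the study when salvage therapy or transplant conditioning begins, and treats that as the end of all data collection, the subject is censored for OS when last known alive. No written censoring rule is needed for that to happen.

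The timing matters. New therapy may follow treatment failure (poor prognosis) or fitness for transplant (better prognosis). Kaplan-Meier assumes that those censored have the same later risk as those still followed, and here that assumption is doubtful in either direction. Collection of new-therapy data, the HR-MDS transformation record and the end of the 28-day safety window are exposed to the same reading.

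**Working it through.** **1. The passages side by side.**

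| Section | What happens at new anticancer therapy |
|---|---|
| 8.2 | Subject leaves the study |
| 6.3.1 | Not an end of 28-day safety follow-up |
| 6.3.2 | Ends efficacy evaluations only; listed apart from study withdrawal; data on the new therapy are collected |
| 6.3.3 | Not an end of survival follow-up |
| Tables 7 and 36 | Not an end of transformation follow-up |
| 11.2 | Not a named reason for leaving the study |

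Section 6.3.2 shows the conflict most clearly. Its collection of new-therapy information stops at study withdrawal. If starting new therapy is itself study discontinuation, collection stops at the moment there is something to collect.

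**2. Disposition at the 13 August 2021 cutoff (Section 1.2.3.1).** The stated percentages reproduce: 79/82 = 96.3% off treatment, 76/82 = 92.7% off study, 67/82 = 81.7% off study because of death.

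- Off study for any reason other than death: 76 - 67 = 9. That is 9/82 = 11.0% of subjects treated and 9/76 = 11.8% of study discontinuations. It is the most that Section 8.2 can have removed by then. The 9 are not split by reason.
- Crude proportion dead among the 82: 67/82 = 81.7% if none of the 9 had died, 76/82 = 92.7% if all had.
- Subjects with a fatal treatment-emergent event: 27 (32.9%). The excess of deaths recorded as study exits is 67 - 27 = 40, which fits deaths being captured beyond the safety window.

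**3. Illustration of the possible bias.** The documents give no switching rate and no survival by switching status, so every parameter here is an assumption: exponential survival with a 4-month median, switch times uniform from 0.5 to 3 months, and a post-switch hazard ratio (HR) of 0.5 to 3 against non-switchers. Medians in months, from 200,000 simulated subjects per setting:

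| Share who switch | Censored at switch | Full follow-up, HR 0.5 | HR 1 | HR 2 | HR 3 |
|---|---|---|---|---|---|
| about 4% | 3.98 to 4.01 | 4.04 | 4.00 | 3.91 | 3.87 |
| about 8% | 4.00 to 4.02 | 4.16 | 4.00 | 3.81 | 3.69 |
| about 22% | 3.98 to 4.00 | 4.42 | 4.00 | 3.52 | 3.27 |
| about 37% | 3.98 to 4.00 | 4.83 | 3.99 | 3.29 | 2.98 |

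Censoring at the switch leaves the estimate near 4.0 whatever happens afterwards. It overstates survival if switchers do worse, understates it if they do better, and is unbiased at HR 1.

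**4. Scale against sampling error.** For 20 uncensored subjects under the same model, the approximate standard error of the median is 0.5 / (f × √n), where f is the density at the median. Here f = 0.5 × ln 2 / 4 = 0.0866, so the standard error is 0.5 / (0.0866 × 4.472) = 1.29 months. The largest shift in the table is 4.00 - 2.98 = 1.02 months, with about 37% switching. At about 8% it is 4.00 - 3.69 = 0.31 months.

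**The case against.** The strongest reply is that Section 8.2 is loosely worded and means study treatment.

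- Section 6.4 lists the start of a new anticancer therapy among reasons for discontinuing treatment, apart from withdrawal of consent from the entire study.
- Section 11.1, which concerns treatment, speaks of subjects with progressive disease remaining on study, so the protocol uses the term loosely elsewhere.
- The summary of changes for Amendment 9 mentions exclusion at new therapy for efficacy follow-up only.
- The follow-up sections agree with one another, and Section 8.2 is the outlier. Survival status can be obtained without visits.
- OS is one of several other measures behind the response rates, all analyses are descriptive, and no sample size, futility rule or toxicity stopping rule uses OS.

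Most of this stands. A reader might infer that Section 8.2 does remove subjects from survival follow-up, that OS is therefore informatively censored and transformation follow-up cut short, and that the 9 non-death exits are evidence of it. The documents do not support that. No passage says follow-up ends for a subject discontinued under Section 8.2, no OS censoring rule is given, and the 9 may have withdrawn consent, been lost or completed follow-up.

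What the reply does not remove is the conflict in the operative text. It shows which reading was probably intended, but a site applying Section 8.2 as written has no pointer to that reading.

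**Conclusion.** The inconsistency is real and the consequence is conditional. Sections 8.2 and 6.3.3 cannot both be followed as written unless leaving the study is taken to leave survival follow-up intact, and the protocol does not say so. If a site acts on the literal wording and stops collecting survival status, the OS estimate could be biased in a direction the documents do not allow one to predict.

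The past loss is at most 9 of 82, with no evidence that any arose this way. Under the stated assumptions, the shift in the median stays below one standard error for a cohort of 20, and with few switchers well below it. The claim that OS is in fact biased goes beyond the text. The severity is minor to moderate: nothing in the design depends on OS, but survival status lost this way may not be recoverable, and Part B may still enroll up to about 20 subjects per disease at each of two dose levels.

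**What to change.** Reconcile Section 8.2 with Sections 6.3.1 to 6.3.3, 6.4, 11.1 and 11.2. State that starting other anticancer therapy does not by itself end participation in safety follow-up, survival follow-up or, for HR-MDS, transformation follow-up, unless the subject withdraws consent for it. In Section 9.6.2 or the SAP, state that OS is not censored at new anticancer therapy. When reporting disposition, split non-death study exits by reason so that any loss by this route can be seen.

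The cost is a short wording change and one line in the analysis text. Telephone contact and record review are already allowed, so no new visits are needed. The change concerns data collection only and takes no position on when study treatment stops or whether other therapy is given.

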8.3 Required Concomitant Medications and Procedures

All subjects will be required to start calcium, calcitriol, and vitamin D supplementation at least 3 days prior to the first dose of CC-90009 in each cycle and continue until \geq 3 days after the last dose of CC-90009 in each cycle. Supplementation may be extended if hypocalcemia occurs (refer to Section 7.2.13.2). Subjects will document (date and time) taking the supplements on diary cards that will be reviewed on Day 1 of each cycle and at the EOT visit.

The calcium/calcitriol/vitamin D supplementation regimen is:

- Calcium carbonate 500 mg elemental calcium PO 3 TID (taken after meals to increase absorption)
 - Alternative preparations of calcium can be substituted but they must equal at least 1200 mg of elemental calcium per day given in divided doses (eg, TID).
 - If the subject is on a proton pump inhibitor (PPI) or has gastric achlorhydria, then administer calcium citrate 630 mg elemental calcium PO TID or closest higher dose based on available strengths.
- Calcitriol 0.25 micrograms PO QD
- Vitamin D supplementation is based on the Screening serum 25-hydroxyvitamin D level:
 - Level < 12 ng/mL excluded from the study
 - Level 12 20 ng/mL Vitamin D3 or D2 50,000 IU weekly
 - Level > 20 ng/mL- Vitamin D3 or D2 1000 IU QD

The risk of TLS with CC-90009 is unknown. Subjects should be adequately hydrated (eg, 2 to 3 liters of oral or IV fluids per day) starting the day prior to CC-90009 administration and continuing through each day of CC-90009 administration.

Subjects given CC-90009 at daily doses \geq 3.6 mg will be administered concurrent dexamethasone per Section 7.2. Subjects enrolled on other dose levels may be administered corticosteroid premedication as per SRC recommendation (eg, at the 3.0 mg dose level on the Days 1-7 and Days 1-10 schedules).

Routine infectious disease prophylaxis including appropriate prophylactic antibiotic, antiviral, anti-pneumocystis, antifungal, or other prophylaxis should be implemented during the study according to institutional standard medical practice.

9 STATISTICAL CONSIDERATIONS

9.1 Overview

The primary objectives of this Phase 1 study are to determine the safety and tolerability of CC-90009, and to define the NTD, MTD, and/or the RP2D of CC-90009. The secondary objectives are to provide information on the preliminary efficacy of CC-90009 in R/R AML and R/R HR-MDS, and to characterize the PK of CC-90009 in plasma and urine.

Data summaries/statistical analyses will be performed by study phase, dose level/dosing regimen and cohort as needed or applicable in the dose escalation phase (Part A) and dose expansion phase (Part B) separately, as well as at dosing regimen(s) used for expansion that include the subjects from both study phases. For retreated subjects, the safety data collected during the initial and the retreated period will be combined for the analysis. The efficacy data will be analyzed and reported for the initial treatment period only.

9.2 Study Population Definitions

The study population definitions are as follows:

- Enrolled Population All subjects who meet all the inclusion/exclusion criteria and are eligible for the study.
- Treated Population All subjects who enroll and receive at least one dose of CC-90009.
- Efficacy Evaluable (EE) Population All subjects who enroll in the study, meet eligibility criteria, complete at least one cycle treatment or receive at least 80% of scheduled dose in Cycle 1, have a baseline leukemia assessment evaluation and at least one valid post-baseline leukemia assessment.
- Pharmacokinetic (PK) Evaluable Population all subjects who enroll and receive at least one dose of CC-90009 and have at least one measurable concentration of CC-90009.
- Biomarker Evaluable (BE) Population all subjects who enroll, receive at least one dose of study drug, and have at least one biomarker assessment, excluding disqualified assessments.

9.3 Sample Size and Power Considerations

During Part A (dose escalation) of the study, a modified accelerated titration design (Simon, 1997) will be used for dose escalation as described in Section 7.2. The total number of subjects in Part 1 will depend on the number of dose escalations required to reach the NTD and cannot be determined in advance. However, the anticipated number of subjects will be approximately 40 to 60.

Following completion of dose escalation (Part A), one or more dosing regimens may be selected with up to approximately 20 evaluable subjects each for R/R AML or R/R HR-MDS at each selected dosing regimen for an expansion phase (Part B). Expansion may occur at the MTD and schedule established in the dose escalation phase, and/or at an alternative tolerable dose and schedule, based on review of safety, PK, and PD data from Part A. Sample sizes are not determined based on power calculation but rather on clinical, empirical and practical considerations traditionally used for exploratory studies of this kind.

At least 13 efficacy evaluable subjects with R/R AML in Part B will be accrued. If the response rate is 30% or more, the probability of seeing no response in the first 13 R/R AML subjects will be less than 1% (Gehan, 1961). If no response is observed out of 13 R/R AML subjects, the enrollment for this cohort will stop for futility. Otherwise, the enrollment will be expanded to up to approximately 20 evaluable subjects each for R/R AML or R/R HR-MDS for this cohort. The 2-sided 95% confidence interval for 20% and 30% response rate is tabulated in Table 14 for different sample size scenarios.

		Sample size			
CI	Response rate	13	20	30	40
0.95	0.2	(0.066, 0.471)	(0.081 ,0.416)	(0.095 ,0.373)	(0.105 ,0.348)
0.95	0.3	(0.122,0.569)	(0.145 ,0.519)	(0.167, 0.479)	(0.181 ,0.454)

Table 14:Confidence Interval for 20% and 30% Response Rate for Different
Scenarios of Sample Size (Wilson score interval)

CI = confidence interval.

Source: Gehan, 1961.

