Statistical analyses will be performed by dose level (Part A) and cohort (Part B) as needed or applicable. All analyses will be descriptive in nature.

All summaries of safety data will be conducted using subjects receiving any CC-90009 (the Treated Population).

The efficacy variables of primary interest are the ORR and CRR. Other preliminary efficacy variables including OS, RFS, PFS, event-free survival, duration of remission, duration of response, and time to remission/response will be summarized. Efficacy analysis will be repeated for the Treated Population and Efficacy Evaluable Population (received a baseline leukemia assessment evaluation, at least one cycle of study treatment or at least 80% of scheduled doses in Cycle 1, and one on-study leukemia assessment evaluation), with the result using the Treated Population considered primary.

All biomarker-related data presentations will be based on treated subjects with at least one biomarker assessment, unless specified otherwise. Descriptive statistics will be presented for baseline and change from baseline of continuous biomarker endpoints, by dosing regimens and/or disease subsets, and overall.

Exploration of PK, PD, safety and activity relationships will be assessed.

During the Part A dose escalation, 72 subjects were enrolled. During the Part B dose expansion, at least 13 efficacy evaluable subjects with R/R AML will be accrued. If the response rate is 30% or more, the probability of seeing no response in the first 13 R/R AML subjects will be less than 1% (Gehan, 1961). If no responder is observed out of 13 R/R AML subjects, the enrollment for this cohort will stop for futility. Otherwise, the cohort will be expanded to up to approximately 20 evaluable subjects each for R/R AML and R/R HR-MDS of a selected dosing regimen if a responder is observed.

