9.6.1 Complete Remission Rate and Objective Response Rate

The CRR is defined as the rate for any type of CR. The ORR is defined as the rate for all response categories, including all types of CRs, MLFS, and PR for AML. For MDS, the ORR includes all

responses (CR, mCR and PR). The efficacy variable of focus will be ORR and CRR. Other measures of clinical activity including overall survival (OS), relapse-free survival (RFS), progression-free survival (PFS), event-free survival, duration of remission, duration of response, time to transformation to AML (HR-MDS subjects only) and time to remission/response will be summarized. Overall response rate and CRR will be summarized using frequency tabulation. Two-sided 95% Clopper-Pearson exact confidence intervals (Clopper, 1934) will be provided for ORR and CRR estimates.

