9.9.3 Stopping Rules Regarding Toxicity in Part B Dose Expansion

During dose expansion phase (Part B), a non-binding Bayesian method will be utilized to monitor excess toxicities defined as the occurrence of AEs during any cycle that would fulfill the DLT criteria specified in Part A or treatment related AEs leading to dose reduction or discontinuation or the occurrence of sepsis. The enrollment in the corresponding expansion cohort will pause to ensure the posterior probability of excess toxicity rate exceeding 25% is not more than 70%, ie, when

Prob (rate of AEs that fulfill the DLT criteria or treatment-related AEs leading to dose reduction or discontinuation or rate of sepsis >0.25|data, a, b) > 0.7.

Where a, b are parameters of Beta distribution. Weakly informative priors, ie, Beta (0.5, 0.5), may be used to calculate the posterior probability. The excess toxicity rate of 25% is established based on clinical inputs with threshold of 70% based on empirical data analysis.

After a minimum of 8 subjects have enrolled and taken at least one cycle of study treatment for a cohort, the posterior distributions of excess toxicity will be calculated on a continuous basis for every subject enrolled (Table 15).

The operating characteristics of the proposed Bayesian safety monitoring plan are detailed in Appendix P.

Number of Subjects	Number of Subjects with AEs fulfilling DLT or other criteria that would prompt potential enrollment pause
8	3
10	4
13	5
17	6
21	7
24	8
28	9
32	10
35	11
39	12

Table 15:Stop Boundaries Based on Stopping Criteria for Each Expansion
Cohort

AE = adverse event; DLT = dose limiting toxicity

Note: Only unique stopping boundaries are presented up to the estimated maximum enrollment of 40 subjects in an expansion cohort.

The SRC will convene regularly (eg, monthly) to review the overall safety/tolerability data and to assess the Bayesian analysis output. Each subject that experiences an AE that meets the above criteria will be reviewed by the SRC, and the overall Bayesian Analysis will be run at that time to guide the SRC on cohort decisions. If the stopping rule is triggered, the SRC will conduct a comprehensive review of available safety, PK, PD, and preliminary efficacy data to make continuation decisions. Decisions to pause enrollment of specific expansion cohort(s) or terminate the study will be determined by the SRC and communicated properly to Investigators, IRBs, and appropriate regulatory authorities.

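### Does it matter that Table 14 shows Wilson intervals while Section 9.6.1 will report Clopper-Pearson intervals?

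*Combined protocol and SAP*

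**What the plan says.** Section 9.3 illustrates response-rate precision in Table 14: "The 2-sided 95% confidence interval for 20% and 30% response rate is tabulated in Table 14 for different sample size scenarios". The table is titled "Confidence Interval for 20% and 30% Response Rate for Different" and continuing "Scenarios of Sample Size (Wilson score interval" (the bracket closes after the last word). The columns are n = 13, 20, 30 and 40.

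Section 9.6.1 sets the reporting method: "Two-sided 95% Clopper-Pearson exact confidence intervals (Clopper, 1934) will be provided for ORR and CRR estimates".

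The same plan limits what Table 14 is for:

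- Section 9.3 on sample size: "Sample sizes are not determined based on power calculation but rather on clinical, empirical and practical considerations".
- Section 9.3 on futility: "If no response is observed out of 13 R/R AML subjects, the enrollment for this cohort will stop for futility".
- Protocol Summary, Statistical Methods: "All analyses will be descriptive in nature".
- Section 9.9.3 on toxicity: the rule uses a Beta posterior, with a Beta(0.5, 0.5) prior that "may be used to calculate the posterior probability".

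**The concern.** A planning table normally shows what the planned analysis will deliver. Here the two sections name different interval methods, neither refers to the other, and the protocol does not say that the reported intervals will be wider than those tabulated. ORR and CRR are the efficacy variables of primary interest, and Table 14 is where the protocol puts figures on their precision. A reader who takes a lower limit of 8.1% from the 20% row at n=20 would later see 5.7% for the same 4 of 20 responders. If a cohort size or a go/no-go threshold had been chosen from the table, the trial would deliver less precision than it was designed for.

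**Working it through.** **Inputs.** Two-sided 95% level, rates 0.20 and 0.30, n = 13, 20, 30, 40, and the Wilson method (Section 9.3, Table 14); the Clopper-Pearson method (Section 9.6.1). z = 1.96.

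**Step 1: reproduce Table 14.** Wilson interval without continuity correction:

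centre = (p + z²/2n) / (1 + z²/n); half-width = z·√(p(1−p)/n + z²/4n²) / (1 + z²/n).

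For p = 0.20, n = 20: z² = 3.8415, so z²/2n = 0.0960, z²/n = 0.1921 and z²/4n² = 0.0024. The centre is 0.2960/1.1921 = 0.2483. The half-width is 1.96 × √(0.0080 + 0.0024)/1.1921 = 1.96 × 0.10198/1.1921 = 0.1677. The limits are 0.081 and 0.416, as printed. The other seven entries also match to rounding:

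| n | 20%: computed | 20%: printed | 30%: computed | 30%: printed |
|---|---|---|---|---|
| 13 | 0.0655, 0.4714 | 0.066, 0.471 | 0.1221, 0.5692 | 0.122, 0.569 |
| 20 | 0.0807, 0.4160 | 0.081, 0.416 | 0.1455, 0.5190 | 0.145, 0.519 |
| 30 | 0.0951, 0.3731 | 0.095, 0.373 | 0.1666, 0.4788 | 0.167, 0.479 |
| 40 | 0.1050, 0.3476 | 0.105, 0.348 | 0.1807, 0.4543 | 0.181, 0.454 |

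The table contains no arithmetic error.

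**Step 2: apply the Section 9.6.1 method.** For x responders of n, the Clopper-Pearson limits are the 0.025 quantile of Beta(x, n−x+1) and the 0.975 quantile of Beta(x+1, n−x). At n=13 the tabulated rates correspond to 2.6 and 3.9 responders, so the nearest whole counts, 3 and 4, are used for both methods.

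| Count | Wilson | Clopper-Pearson | Extra width |
|---|---|---|---|
| 3/13 | 0.082, 0.503 | 0.050, 0.538 | 15.9% |
| 4/13 | 0.127, 0.576 | 0.091, 0.614 | 16.4% |
| 4/20 | 0.081, 0.416 | 0.057, 0.437 | 13.1% |
| 6/20 | 0.145, 0.519 | 0.119, 0.543 | 13.5% |
| 6/30 | 0.095, 0.373 | 0.077, 0.386 | 11.0% |
| 9/30 | 0.167, 0.479 | 0.147, 0.494 | 11.1% |
| 8/40 | 0.105, 0.348 | 0.091, 0.356 | 9.6% |
| 12/40 | 0.181, 0.454 | 0.166, 0.465 | 9.6% |

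Every limit moves outward, by 0.9 to 3.8 percentage points; at n=20 the shift is 2.1 to 2.7 points.

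**Step 3: is the Wilson figure too optimistic?** Exact coverage is the sum of binomial probabilities over the counts whose interval contains the true rate.

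| n, true rate | Wilson | Clopper-Pearson |
|---|---|---|
| 13, 20% | 97.0% | 99.3% |
| 13, 30% | 97.2% | 97.2% |
| 20, 20% | 95.6% | 97.8% |
| 20, 30% | 97.5% | 97.5% |

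At these two sizes Wilson already exceeds its nominal 95%. In two of the four cells the wider interval gains no coverage at all.

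**Step 4: does anything depend on the table?** The 13-subject futility look rests on 0.7^13 = 0.0097, which is below 1% and uses no interval. The toxicity boundaries come from a Beta posterior. The cohort size of about 20 is stated to be a practical choice. None of these would change if Table 14 were recomputed.

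**The case for a change.** The strongest case for acting is that the gap is largest where it is most relevant. Response is assessed by different criteria in the two diseases, and each regimen takes up to about 20 evaluable subjects per disease, so the n=13 and n=20 columns are the closest to the eventual analyses; there the extra width is 13% to 16%. The n=13 column also shows rates that no whole count can produce. The remedy would be one table, with no effect on subjects or data. In addition, Wilson is not uniformly safe: exact coverage falls to 93.0% at n=30 with a 30% rate, and to 92.8% and 94.4% at n=40 with 20% and 30%.

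The mismatch and its size stand. Three points weaken the case for action:

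- The 16% figure belongs to n=13, where the futility rule ends enrolment only with zero responders. Counts such as 3 or 4 of 13 lead on towards about 20 subjects, where the excess is about 13%.
- The sub-nominal coverage occurs at n=30 and n=40, above the planned size of a single disease group. Pooling of the two diseases is described for safety, PK and PD, not for response.
- Table 14 was never an exact forecast of the reported interval. Its n=13 and n=20 match targets for evaluable subjects, while the primary efficacy result uses the Treated Population, whose denominator may be larger.

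**Conclusion.** No change to the plan is needed. This is a presentational inconsistency between an illustrative table that names its method and an analysis section that names another. An analyst will compute Clopper-Pearson intervals because Section 9.6.1 says so, and nobody would read Table 14 as the reporting rule. The reported intervals will be about 13% wider than tabulated at n=20, and 9.6% to 16.4% wider over the whole table, when compared at the same whole counts and denominators.

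The conclusion rests on two things: the operative method in Section 9.6.1 is unambiguous, and no sample size, stopping rule or hypothesis test uses these intervals. It would be different if a cohort size or an efficacy threshold had been derived from Table 14, and the protocol shows no such use. Relabelling the n=13 column to 23% and 31% would also have a cost, because the rows would no longer compare one rate across sample sizes and that column would lose the 30% rate used for the futility look.
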